4.2. CDMS

Datasets to be analyzed

Dataset name	Data rows, unique identifier	Data rows unique type	Relevant for SAP and SAR	Parent CRF In case of embedded log	Notes
adverse_event	record_id	Event	Yes	n.a.	
baseline_general	record_id, patient_id patient_display_id_full	Patient	Yes	n.a.	
cardiac_diagnostics	record_id, patient_id patient_display_id_full	Patient	Yes	n.a.	
ecg_recording	record_id, patient_id patient_display_id_full	Patient	Yes	n.a.	
enrollment	record_id, patient_id patient_display_id_full	Patient	Yes	n.a.	
internal_evaluation	record_id, patient_id patient_display_id_full	Patient ¹	Yes	n.a.	
medical_history	record_id, patient_id patient_display_id_full	Patient	Yes	n.a.	
termination	record_id, patient_id patient_display_id_full	Patient	Yes	n.a.	

Other Datasets

Dataset name	Data rows, unique identifier	Data rows unique type	Relevant for SAP and SAR	Parent CRF In case of embedded log	Notes
deviation_form_bio_log	record_id, site ID	Site	No	n.a.	Log per Site- for deviation_form_bio
deviation_form_bio	record_id	Event	No	n.a.	
deviation_form_site	record_id	Event	No	n.a.	Might be related to another CRF via parent_record_id
hospitalization_log	record_id, patient_id patient_display_id_full	Event	No	adverse_event	
monitor_evaluation	record_id, patient_id patient_display_id_full	Patient ²	No	n.a.	

¹ Has to be checked during Blind Review, because technically multiple entries per patient are possible

² Technically multiple entries per patient are possible

5. General Statistical Procedures

5.1. Descriptive analyses

CIP chapter 11.1 Statistical design, method and analytical procedures

Exploratory data analysis will be used to describe the patient population....

For continuous variables descriptive statistics (mean, standard deviation, minimum, 1. quartile, median, 3. quartile and maximum) will be calculated. For nominal variables absolute numbers and relative frequencies based on the non-missing data will be determined. Ordinal data are described by the 1st quartile, median, and 3rd quartile as well as the absolute numbers and relative frequencies based on the non-missing data of each category.

For illustration, see the following standard tables with and without subgroup analyses based on dummy data.

Nominal – dichotomous data

Variable (N total = 10)	Category	N non-missing	Absolute frequency	Relative frequency [%]
Gender	Female	9	3	33.3
History of atrial fibrillation	Yes	8	4	50.0

Variable (N total = 10)	Category	Group Type of recording	N non-missing	Absolute frequency	Relative frequency [%]
Gender	Female	3-Patch Holter (N group = 4)	4	1	25.0
		10-Patch Holter (N group = 4)	4	2	50.0
		All	9	3	33.3
History of atrial fibrillation	Yes	3-Patch Holter	4	2	50.0
		10-Patch Holter	4	2	50.0
		All	8	4	50.0

Nominal data – more than two categories

Variable (N total = 10)	N non-missing	AV block I N(%)	AV block II N(%)	AV block III N(%)
Type of AV block	8	3 (37.5%)	3 (37.5%)	2 (25.0%)

Variable (N total = 10)	Group Type of recording	N non-missing	AV block I N(%)	AV block II N(%)	AV block III N(%)
Type of AV block	3-Patch Holter (N group = 4)	3	1 (33.3%)	1 (33.3%)	1 (33.3%)
	10-Patch Holter (N group = 4)	4	2 (50.0%)	1 (25.0%)	1 (25.0%)
	All	8	3 (37.5%)	3 (37.5%)	2 (25.0%)

Scale / metric data

Variable (N total = 10)	N non- missing	Mean	SD	Min	Lower quartile	Median	Upper quartile	Max
Age [years]	9	56.1	15.9	25.0	50.0	60.0	66.0	77.0
Weight [kg]	8	78.5	13.9	55.0	69.5	78.5	89.0	99.0

Variable (N total = 10)	Group Type of recording	N non- missing	Mean	SD	Min	Lower quartile	Median	Upper quartile	Max
Age [years]	3-Patch Holter (N group = 4)	4	61.8	11.2	50.0	55.0	60.0	68.5	77.0
	10-Patch Holter (N group = 4)	4	50.3	21.5	25.0	32.5	53.0	68.0	70.0
	All	9	56.1	15.9	25.0	50.0	60.0	66.0	77.0
Weight [kg]	3-Patch Holter	3	85.0	7.0	77.0	77.0	88.0	90.0	90.0
	10-Patch Holter	4	76.0	18.5	55.0	62.5	75.0	89.5	99.0
	All	8	78.5	13.9	55.0	69.5	78.5	89.0	99.0

Ordinal data

Identical tables as for metric data but without mean and SD

5.2. Inferential analyses

CIP chapter 11.2 Sample Size

For this study, no statistical hypotheses can be formulated.

5.3. Significance level

A two-sided P value < 0.05 is considered to indicate statistical significance. No adjustment for multiple testing is foreseen. All analyses except are considered to be exploratory.

5.4. Missing Data

CIP chapter 11.10 Handling of missing, unused and spurious data

Missing or spurious data will not be imputed.

Missing data will not be imputed. Free text will be used to clarify other data.

Spurious data will be clarified via the query management, i.e. corrected after approval of an investigator. Remaining outliers will be identified during the review of the data before data base closure. In case of a clear evidence of a measurement error, the Statistical Analysis Plan will be updated in order to avoid any bias. Spurious data, which were not clarified by the query process before database closure, will be indicated. If appropriate, analyses will be performed both with /without such data.

5.5. Exclusion of data from confirmatory data analysis

CIP chapter 11.12 Exclusion of data from the confirmatory data analysis

No data is allowed to be collected and included in the absence of a documented consent.

5.6. Subgroups

CIP chapter 11.8 Specification of subgroups

There are no pre-defined sub-groups.

5.7. Interim analyses

CIP chapter 11.5 Provision for an interim analysis

As there is no hypothesis to test, no comprehensive interim analysis is planned at a certain point in time. The acquired data will be continuously forwarded to the technical department for analysis.

5.8. Software

All analyses will be carried out using validated software, e.g. SAS version 9.4 or upgrades.

6. Specific Study Dates

6.1. Enrollment date

CIP chapter 8.3.5 Point of enrollment and study termination

The point of enrollment is defined as the time of signature of the informed consent form by the patient. Study related procedures, documentation and collection/following of adverse events will start from this time on.

Data file, identifier patient_display_id_full	Variable name	Variable label	Variable level	Nominal values
enrollment	DMICDT	Patient: Date of informed consent signature	date	n.a.

6.2. Date of baseline assessment

CIP chapter 9.2 Enrollment/Baseline visit

After a subject has been enrolled, the following data have to be collected and entered in the respective CRF:

- Date of baseline assessment

Data file, identifier patient_display_id_full	Variable name	Variable label	Variable level	Nominal values
baseline	SVBLDT	Date of baseline assessment	date	n.a.

6.3. Termination date

CIP chapter 8.3.5 Point of enrollment and study termination

The patient's study participation ends regularly at the moment when the last study procedure according to protocol has been completed. The point of non-regular study termination can be the following:

- Date of withdrawal of consent
- Date of patient death
- If patient is a drop-out, the date of last patient related patient contact.

Study related procedures and data collection must end at the day of study termination.

Data file, identifier patient_display_id_full	Variable name	Variable label	Variable level	Nominal values
termination	DSTRDT	Date of study termination	date	n.a.

7. Analysis Sets

7.1. Analysis Set: Enrolled patients

All patients with valid informed consent are included in the analysis set of all enrolled patients

Data file, identifier patient_display_id_full	Variable name	Variable label	Variable level	Nominal values
enrollment	DMICDT	Patient: Date of informed consent signature	date	n.a.
enrollment	DMSUBSPS	Patient signed the informed consent personally	nominal	 Yes  No
enrollment	DMRPRSPS	A legally authorized representative signed the informed consent	nominal	 Yes  No
enrollment	DMSUBDPS	Patient dated the informed consent personally	nominal	 Yes  No
enrollment	DMRPRDPS	A legally authorized representative dated the informed consent	nominal	 Yes  No
data_SAR	analysis_set_enrol_SAR ³	Analysis set of all enrolled patients	nominal	 Yes  No

7.2. Analysis Set: Enrolled Patients with any ECG

All patients from the analysis set of enrolled patients with any documented ECG are included in the analysis set of enrolled patients with ECG.

Data file, identifier patient_display_id_full	Variable name	Variable label	Variable level	Nominal values
ecg_recording	EGEPSSDT	Start Date and Time EPS ECG	date	n.a.
	EGEPSEDT	End Date and Time EPS ECG	date	n.a.
	EGEPDOSD	Start Date and Time EPS DLO-ECG	date	n.a.
	EGEPDOED	End Date and Time EPS DLO-ECG	date	n.a.
	EGBMTSDT	Start Date and Time BMT ECG	date	n.a.
	EGBMTEDT	End Date and Time BMT ECG	date	n.a.
	EGBMDOSD	Start Date and Time BMT DLO-ECG	date	n.a.
	EGBMDOED	End Date and Time BMT DLO-ECG	date	n.a.
data_SAR	analysis_set_ecg_SAR ⁴	Analysis set of all enrolled patients compliant with all in- and exclusion criteria and with any ECG data available	nominal	 Yes  No

8. Data for a CONSORT diagram

All analyses are performed for the analysis set of all enrolled patients⁵.

8.1. Enrollment

- Date of First-Patient-In
- Date of Last-Patient-In
- Number of patients
- Number of patients per site

Inclusion criteria

Data file, identifier patient_display_id_full	Notes	Variable name	Variable label	Variable level	Nominal values
enrollment	descriptive	TIINCL01	Patient is able to understand the nature of the study and willing to provide written informed consent	nominal	 Yes  No
		TIINCL02	Patient is willing and able to attend Holter ECG procedure following a visit	nominal	 Yes  No
		TIINCL03	Patient with pacemaker or ICD and ventricular stimulation > 30% or	nominal	 Yes  No
		TIINCL04	Frequent Ventricular Extrasystoles (VES) (incl. Bigeminus) or	nominal	 Yes  No
		TIINCL05	Atrioventricular Reentrant Tachycardia (AVRT) / Wolff-Parkinson-White (WPW) syndrome or	nominal	 Yes  No
		TIINCL06	Atrioventricular Nodal Reentrant Tachycardia (AVNRT) or	nominal	 Yes  No
		TIINCL07	Sinus Tachycardia at rest or	nominal	 Yes  No
		TIINCL08	Atrial Flutter or	nominal	 Yes  No
		TIINCL09	Any form of Ventricular Tachycardia (VT) or	nominal	 Yes  No
		TIINCL10	Silent / paroxysmal / persistent / permanent AF or	nominal	 Yes  No
		TIINCL11	Brugada syndrome or	nominal	 Yes  No
		TIINCL12	Long QT syndrome or	nominal	 Yes  No
		TIINCL13	Right Bundle Branch Block (RBBB) or	nominal	 Yes  No
		TIINCL14	Left Bundle Branch Block (LBBB) or	nominal	 Yes  No
		TIINCL15	Myocardial Ischemia / Acute Myocardial Infarction or	nominal	 Yes  No
		TIINCL16	Other abnormal QRS(T) complex, ST segment or T-wave morphology	nominal	 Yes  No

Exclusion criteria

Data file, identifier patient_display_id_full	Notes	Variable name	Variable label	Variable level	Nominal values
enrollment	descriptive	TIEXCL01	Any condition which precludes the patient's ability to comply with the study requirements.	nominal	 Yes  No
		TIEXCL02	Known allergy to patch electrodes	nominal	 Yes  No
		TIEXCL03	Pregnant or breast feeding	nominal	 Yes  No
		TIEXCL04	Less than 18 years old	nominal	 Yes  No
		TIEXCL05	Participating in another interventional clinical investigation according to the definition	nominal	 Yes  No

8.2. Termination

- Date of First-Patient-Out
- Date of Last-Patient-Out

Data file: Identifier patient_display _id_full	Notes	Variable name	Variable label	Variable level	Nominal values
termination	descriptive	DSRTRM	Regular study termination	nominal	 Yes  No
termination	Descriptive for DSRTRM= Yes	DSETRREA	Reason for early study termination	nominal	 Patient moved away from investigational center  Patient withdrew consent to study participation  Patient death  Drop-out according to protocol  Enrollment failure  Other

Data file: Identifier patient_display _id_full	Notes	Variable name	Variable label	Variable level	Nominal values
enrollment	Case listings for DSRTRM = Yes	DMSUBIC	Date of informed consent	date	n.a.
termination		DSTRDT	Date of study termination	date	n.a.
		DSRTRM	Regular study termination	nominal	 Yes  No
		DSETRREA	Reason for early study termination	nominal	 Patient moved away from investigational center  Patient withdrew consent to study participation  Patient death  Drop-out according to protocol  Enrollment failure  Other
		COETRREA	Please specify reason for early termination	text	...

Data file: Identifier patient_display _id_full	Notes	Variable name	Variable label	Variable level	Nominal values
data_SAR	descriptive	FU_duration_SAR ⁶	Days from enrollment to termination	scale	n.a

Data file: Identifier patient_display _id_full	Notes	Variable name	Variable label	Variable level	Nominal values
enrollment	Case listings for DSETRREA = Drop-out according to protocol	DMSUBIC	Date of informed consent	date	n.a.
termination		DSTRDT	Date of study termination	date	n.a.
		DSRTRM	Regular study termination	nominal	 Yes  No
		DSETRREA	Reason for early study termination	nominal	 Patient moved away from investigational center  Patient withdrew consent to study participation  Patient death  Drop-out according to protocol  Enrollment failure  Other
		DSDRPPRO	Please specify reason for early termination	nominal	 Patient is unable or unwilling to proceed with the Holter ECG recording due to discomfort when wearing the electrodes.  Patient is unable or unwilling to proceed with the Holter ECG recording due to discomfort or dizziness during the Body Motion Test.  Holter ECG recording does not take place for any reasons within 14 days after enrollment.  For 10-Patch Holter ECG recording: DLO does not take place for any reasons within 14 days after BMT  Other
		CODRPPRO	Please specify "Drop-out according to protocol- Other"	text	...

9. Data of interest

CIP chapter 7.3 Further data of interest

- Demographic data, medical history, ECG diagnosis
- Adverse Events related to the study procedure
- Optional: chest x-ray, only if already available and part of a procedure (e.g. implantation) that occurred prior to enrollment

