9.5 Termination

The patient's study participation ends regularly at the moment when the last study procedure according to protocol has been completed. The CRF 'Termination' has to be completed.

In case of any premature study termination, the CRF 'Termination' has to be completed with the reason for study termination. If the Holter ECG could not be completed successfully, the reason must be provided.

Follow-up of patients who have withdrawn consent is covered in section 8.3.4.2.

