11.3 Expected drop-out rate

It is expected that at least 10 % of the enrolled patients can only be partly included or not at all in the analysis of data, e.g. due to withdrawal of consent, refusal to participate in the Holter ECG or premature termination without documentation of the intended ECG pattern.

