9.2. Variables

Baseline / Demographic data

Data file, identifier patient_display_id_full	Notes	Variable name	Variable label	Variable level	Nominal values
baseline	descriptive	DMSEX	Gender	nominal	 Male  Female
	descriptive	DMAGE	Age [Years]		

Baseline / Physical examination

Data file, identifier patient_display_id_full	Notes	Variable name	Variable label	Variable level	Nominal values
baseline	descriptive	VSHGHT	Height [cm]	scale	n.a.
	descriptive	VSWGHT	Weight [kg]		

Baseline / Physical examination / device

Data file, identifier patient_display_id_full	Notes	Variable name	Variable label	Variable level	Nominal values
baseline	descriptive	PRIMDVTY	Type of implanted device	nominal	 Single Chamber ICD  VR-T DX System  Dual Chamber ICD  Single Chamber PM  Dual Chamber PM  Implantable Loop Recorder  No device

Chest X-Ray

Data file, identifier patient_display_id_full	Notes	Variable name	Variable label	Variable level	Nominal values
Baseline	descriptive for PRIMDVTY = No device	PRCHXR	Chest X-ray of original procedure available	nominal	 Yes  No

Cardiac diagnostic / ECG history

Data file, identifier patient_display_id_full	Notes	Variable name	Variable label	Variable level	Nominal values
cardiac_diagnostic	descriptive	EGHRT	Heart rate [bpm]	scale	n.a.
	descriptive	EGPRI	PR interval [ms]	scale	n.a.
	descriptive	EGQRS	QRS width (intrinsic) [ms]	scale	n.a.
	descriptive	EGQRSM	QRS morphology	nominal	 Normal  LBBB  RBBB  Indeterminate
	descriptive	CVEGARH	Atrial rhythm during ECG recording	nominal	 Sinus rhythm  Atrial fibrillation  Atrial flutter/other SVT  Atrial paced rhythm  Other
	Case listings for CVEGARH = Other	COEGARH	Specification of other atrial rhythm during ECG recording	text	...
	descriptive	CVEGVRH	Ventricular rhythm during ECG	nominal	 Intrinsic - atrial conducted  Intrinsic - escape rhythm  Ventricular paced rhythm  Other
	Case listings for COEGVRH = Other	COEGVRH	Specification of other ventricular rhythm during ECG recording	text	...

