	descriptive	MHAVA	History of other atrial/supraventricular arrhythmias	nominal	 Yes  No
	descriptive for MHAVA = Yes	MHAFL	History of atrial flutter	nominal	 Yes  No
		MHAT	History of atrial tachycardia	nominal	 Yes  No
		MHSVT	History of supraventricular tachycardia	nominal	 Yes  No
		MHAVAOTH	History of other type of atrial/supraventricular arrhythmias	nominal	 Yes  No
	Case listings for MHAVAOTH = Yes	COAVAOTH	Specification of other type of atrial/supraventricular arrhythmia	text	...

Data file, Identifier patient_display_id_full	Notes	Variable name	Variable label	Variable level	Nominal values
medical_history	descriptive	MHVA	History of ventricular arrhythmia	nominal	 Yes  No
	descriptive for MHVA = Yes	MHNSUVT	Non-sustained ventricular tachycardia	nominal	 Yes  No
		MHSUVT	Sustained ventricular tachycardia	nominal	 Yes  No
		MHVFB	Ventricular fibrillation	nominal	 Yes  No
		MHVAOTH	History of other ventricular arrhythmia	nominal	 Yes  No
	Case listings for MHVAOTH = Yes	COVAOTH	Specification of history of other ventricular arrhythmia	text	...

Medical history / heart failure

Data file, identifier patient_display_id_full	Notes	Variable name	Variable label	Variable level	Nominal values
medical_history	descriptive	MHHF	History of heart failure	nominal	 Yes  No
	descriptive for MHHF = Yes	CVNYHA	Current NYHA classification	nominal	 I  II  III  IV

Adverse Events related to the study procedure

Data file, Identifier record_id	Notes	Variable name	Variable label	Variable level	Nominal values
adverse_event	No reporting	AERELSPR	AE is related to an additional study procedure	nominal	 Not related  Unlikely  Possible  Probable  Causal relationship
	Case listing for all AEs except AERELSPR = not related	AESDTH	Event led to death	nominal	 Yes  No

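### SAP 8.2 filters the early-termination reason table and case listing on regular termination (DSRTRM = Yes), so both select the wrong patients

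*SAP*

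**What the plan says.** SAP section 8 supplies the data for a CONSORT diagram, for all enrolled patients. Within 8.2:

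- DSRTRM records whether termination was regular (Yes/No) and is tabulated without a filter.
- DSETRREA records the reason for early termination, in six categories: moved away, withdrew consent, death, drop-out according to protocol, enrollment failure, other. Its note is "Descriptive for DSRTRM= Yes".
- A listing of consent date, termination date, DSRTRM, DSETRREA and the free-text reason COETRREA is headed "Case listings for DSRTRM = Yes".
- A separate listing is filtered on DSETRREA being drop-out according to protocol and does not use DSRTRM.

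SAP 6.3 says that participation ends regularly once the last protocol procedure is completed. It then introduces withdrawal of consent, death and drop-out with "The point of non-regular study termination can be the following". Protocol 9.5 says that on premature termination the Termination CRF has to be "completed with the reason for study termination".

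Three further filters in SAP 9.2 are relevant:

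- The listing of other ventricular rhythms is headed "Case listings for COEGVRH = Other", although COEGVRH is the free-text field being listed. The parallel atrial row uses the coded field: "Case listings for CVEGARH = Other".
- The listing of other bundle branch blocks is filtered on `MHBBTYP`, whereas the variable defined one row above is `MHBBBTYP`.
- The row on availability of a chest X-ray is limited to patients whose device type (PRIMDVTY) is no device. Protocol 7.3 gives implantation as its example of the procedure that an X-ray may come from.

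**The concern.** The reason for early termination is tabulated and listed for the patients who did not terminate early. Section 8.2 is the only place in the SAP where patient disposition is reported by reason. If the programmer follows it literally, the report will show an empty reason table beside a non-zero count of early terminations, and a listing of regular completers with blank reasons.

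Withdrawal of consent is the most visible loss. Protocol 11.3 names it first among its examples of why patients "can only be partly included or not at all in the analysis of data", yet it would appear in no output by reason. Disposition also matters here because Protocol 8.1.4 allows some drop-outs to be replaced, so total enrollment may exceed the plan and a reader will want to know why patients left.

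**Working it through.** The plan gives no figure to reproduce; this is a check of filter logic.

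**Step 1: which value of DSRTRM goes with a reason?**

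| Source | Content | Implication |
|---|---|---|
| SAP 8.2, label of DSRTRM | Regular termination, Yes/No | Yes = regular, No = not regular |
| SAP 6.3 | Withdrawal, death, drop-out are non-regular | These patients have DSRTRM = No |
| SAP 8.2, label of DSETRREA | Reason for early termination | Applies to DSRTRM = No |
| Protocol 9.5 | Reason required on premature termination | Reason is filled in when DSRTRM = No |

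Nothing in the SAP recodes DSRTRM. It is a raw database variable: SAP 1.2 gives derived variables the suffix _SAR, and DSRTRM has neither that suffix nor a footnote marker.

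**Step 2: apply each filter.** Let N be the number enrolled and k the number of early terminations, with DSETRREA blank for regular completers. SAP 5.1 bases nominal tables on non-missing data.

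- DSRTRM = Yes selects N − k patients. Non-missing reasons: 0. Early terminations listed: 0 of k.
- DSRTRM = No selects k patients. Non-missing reasons: k. Early terminations listed: k of k.

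For illustration, take the planned N = 100 (Protocol 11.2) and assumed values of k:

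| k (assumed) | Listed under Yes | Reasons under Yes | Listed under No | Reasons under No |
|---|---|---|---|---|
| 5 | 95 | 0 | 5 | 5 |
| 10 | 90 | 0 | 10 | 10 |
| 20 | 80 | 0 | 20 | 20 |

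The reversal does not depend on k. The documents give no early-termination rate. The 10 % in Protocol 11.3 is the share of patients not fully included in the analysis, which is a different quantity.

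**Step 3: what survives?** Of the 6 reason categories, 1 (drop-out according to protocol) has its own listing, so 6 − 1 = 5 lose both table and listing. Two of the 5 have partial substitutes elsewhere:

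- Death may appear in the SAP 9.2 adverse event output, "Case listing for all AEs except AERELSPR = not related", unless the event was rated not related.
- Enrollment failure may show in the inclusion and exclusion counts of SAP 8.1, if the term refers to eligibility; the documents do not define it.

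That leaves 5 − 2 = 3 categories (moved away, withdrew consent, other) with no output by reason. Of the three non-regular types in SAP 6.3, two (withdrawal and death) lose their listing. The total k is still available from the unfiltered DSRTRM row.

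**Step 4: the SAP 9.2 filters.**

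- COEGVRH is free text, so a filter on its being equal to Other would not select the patients for whom the coded field CVEGVRH is Other. CVEGVRH is defined in the row above and has that category.
- `MHBBTYP` is not defined anywhere in the SAP.
- The chest X-ray filter removes every patient with a device, including everyone in condition 1, which requires a pacemaker or ICD (Protocol 8.3.2). The item's own label refers to the original procedure, which sits oddly with a restriction to patients without a device.

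**The case against.** The strongest case is about weight. The labels make the intent plain, and an empty reason table next to a non-zero count of early terminations would probably be noticed at first run. The reasons are still collected, so nothing is lost from the database, and Protocol 11.7 allows deviations from the statistical plan to be explained in the report. The study has no hypotheses, no pass/fail criteria and no planned publication. All of this stands and limits the consequence to disposition reporting. It does not make the rule right: SAP 1.1 says that the document gives detailed instructions, and correcting it beforehand is simpler than reporting a deviation afterwards.

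On certainty, the CRF branching is not shown, so an empty reason table is an inference from the label and Protocol 9.5. That section also asks for a reason when the Holter recording could not be completed, but this is not the same item as the reason for early termination. The inference is sound, and the listing selects the wrong patients whether or not it holds.

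A not-equal sign lost in converting the PDF to text cannot be strictly excluded. It is unlikely: the same condition appears in two separate tables, the SAP writes = No when it wants the negative group (the Body Motion Test rows in 10.2), and it expresses exclusion in words in the adverse event listing.

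The category count measures which outputs fail, not how many patients are affected. That is correct, and no patient count is claimed. It is also fair that the chest X-ray item is optional and implantation only an example in Protocol 7.3, so that filter is a query rather than a proven error.

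**Conclusion.** The concern holds. Both DSRTRM filters in SAP 8.2 are inverted. As written, the listing shows N − k regular completers and none of the k early terminations, and the reason table has no valid entries, on the assumption that reasons are blank for regular completers. A reason recorded under DSRTRM = Yes would itself be a data inconsistency. Five of the six reason categories lose both table and listing, and three of those have no substitute anywhere in the SAP.

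This should be fixed before the report is programmed, but its reach is limited: the output is descriptive, the endpoint and sample size are untouched, and the overall number of early terminations and the listing of protocol drop-outs remain. The two variable-name slips in SAP 9.2 are clear but minor. The chest X-ray filter needs an explanation or a change.

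**What to change.** In SAP 8.2, change the filter on the DSETRREA table and on the general termination listing to DSRTRM = No.

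In SAP 9.2:

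- Filter the other-ventricular-rhythm listing on CVEGVRH = Other, to match the atrial row.
- Filter the other-bundle-branch-block listing on `MHBBBTYP` = Other.
- Remove, correct or justify the restriction of the chest X-ray row to patients without a device. Any replacement should not exclude patients without a device who have an eligible X-ray from another earlier procedure.

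The cost is two filter values, two variable names and one filter to settle. Data collection and the endpoint analysis do not change.
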